8.2.1 Inclusion criteria for randomization

- At least partial response on induction treatment
- Hematological recovery defined as ANC ≥ 1.0 x 10⁹ /L and platelets ≥ 75 x 10⁹ /L
- ♦ Completion of 9 cycles of induction treatment *OR* a minimum of 6 cycles in case there is non-hematological toxicity NOT related to ixazomib citrate, requiring discontinuation of induction therapy (for definitions of non-hematological toxicity requiring discontinuation see appendix G for thalidomide and appendix H for dexamethasone)

8.2.2 Exclusion criteria for randomization

- Non-hematological toxicity grade 2 or more related to ixazomib citrate at time of randomization.
- Significant hepatic dysfunction (total bilirubin ≥ 1.5 x ULN μmol/l or transaminases ≥ 3 times normal level) except patients with Gilbert's syndrome as defined by > 80% unconjugated bilirubin.
- Creatinine clearance <30 ml/min or Calculated Glomerular Filtration Rate [ml/min/1.73m²]
 <30.

- Evidence of current uncontrolled cardiovascular conditions, including uncontrolled hypertension, uncontrolled cardiac arrhythmias, symptomatic congestive heart failure, unstable angina, or myocardial infarction after registration.
- Severe pulmonary dysfunction (Modified Medical Research Counsil dyspnea scale classification III-IV).
- Uncontrolled infection at time of randomization.

9 Treatment

9.1 Induction treatment with ixazomib citrate/thalidomide/low dose dexamethasone

9.1.1 Treatment schedule

Induction therapy should start within 4 weeks after patient registration. Patients will receive 9 cycles of ixazomib citrate (4 mg) on days 1, 8, 15 of a 28-day cycle and a daily dose of thalidomide (100 mg) continuously plus dexamethasone (40 mg) on days 1, 8, 15 and 22.

Agent	Dose/day	Route of administration	Days
Ixazomib citrate	4 mg	p.o	1,8 and 15
Thalidomide	100 mg	p.o	1 - 28
Dexamethasone	40 mg	p.o.	1, 8, 15 and 22

After cycle 1, 3, 5, 7 and 9 evaluation will take place. In case of progressive disease after cycle 3, 5, 7 or 9 patients will go off protocol treatment.

9.1.2 Dose adjustments during treatment with ixazomib citrate/thalidomide/low dose dexamethasone

During the first cycle, the first dose of ixazomib citrate will always be administered in a 100% dose, independently of blood cell counts. At day 8 and 15 doses will be adjusted according to the tables and the flow sheet in appendix F (in case platelets are $\leq 30 \times 10^9 / L$ and or neutrophils are $\leq 0.5 \times 10^9 / L$). For next cycles to begin the patient must meet the following criteria:

- ANC ≥ $1.0x10^9/L$
- platetelets ≥ 75x10⁹/L
- other non-hematological toxicities (except alopecia) ≤ CTCAE grade 1 or the patient's baseline condition.

If the patient fails to meet the above-cited criteria for initiation of the next cycle of treatment, dosing should be delayed for 1 week. At the end of that time, the patient should be re-evaluated to determine whether the criteria have been met. If the patient continues to fail to meet the above-cited criteria, delay therapy and continue to re evaluate. The maximum delay before treatment should be discontinued will be 6 weeks. See the tables and the flow chart in appendix F.

Instructions for intake and dose reduction for ixazomib citrate, thalidomide and dexamethasone are given appendix F, G, and H respectively.

9.1.3 Supportive care

- All patients will receive thrombosis prophylaxis with "aspirin" (acetylsalicylic acid 75 or 80 mg or carbasalate calcium 100 mg) during the entire period of induction therapy. Patients with intolerance to "aspirin" or a positive history of a venous thrombosis event will receive thrombosis prophylaxis with low molecular weight heparin (LMWH). The treating physician might prefer LMWH instead of aspirin, also in patients other than with intolerance to "aspirin" or a positive history of venous thrombosis, which is allowed. Both aspirin and LMWH will be discontinued if platelets fall below 50 x 10⁹/L.
- All patients will receive Herpes Zoster prophylaxis with valacyclovir at a dose of 500 mg two times daily during the induction and maintenance treatment until 1 month after the last administration of ixazomib citrate.
- Patients will receive prophylactic therapy with antibiotics at the discretion of the treating physician. In case the patient experiences an infectious event requiring admission during induction therapy, prophylactic antibiotics (type of antibiotics according to local protocols) are mandatory during the following courses of induction therapy. Systemic treatment, within 14 days before the first dose of ixazomib, with strong CYP3A inducers (rifampin, rifapentine, rifabutin, carbamazepine, phenytoin, phenobarbital), or use of Ginkgo biloba or St. John's wort.. In addition, cotrimoxazole is allowed. For further details also see paragraph 9.3.
- Treatment with bisphosphonates, either pamidronate 30 mg/month or zoledronate 4
 mg/month is advised and will be continued for at least 2 years or longer at the discretion of the treating physician.
- Myeloid growth factors (eg, granulocyte colony stimulating factor [G-CSF], granulocyte macrophage-colony stimulating factor [GM-CSF]) are permitted, according to institutional practice

9.2 Maintenance treatment with ixazomib citrate or Placebo maintenance

9.2.1 Treatment schedule

After the response evaluation of the last ixazomib citrate -thalidomide-low dose dexamethasone cycle patients will be randomized. In randomized patients, maintenance treatment with either ixazomib citrate or placebo will be started within a maximum of 12 weeks after start of the last ixazomib citrate - thalidomide-low dose dexamethasone cycle, at a dose of 4 mg on days 1, 8, and 15 of a 28-day cycle.

Maintenance cycles will be repeated at 28-days intervals until progression or when a medical condition occurs that requires discontinuation of the treatment.

Agent	Dose/day	Route	Days
Ixazomib citrate or	4 mg*	p.o	1, 8 and 15
placebo			

^{*}or at the dose level during induction therapy in case dose reductions were required during induction therapy

Response evaluation will take place as described in chapter 10.

9.2.2 Dose adjustments during maintenance treatment with ixazomib citrate

Dose reduction instructions for ixazomib citrate are given in appendix F.

9.3 Excluded Concomitant Medications and Procedures

The following medications and procedures are prohibited during the study:

Systemic treatment with any of the following metabolizing enzyme inducers should be avoided unless there is no appropriate alternative medication for the patient to use. (Rationale: If there were to be a drug-drug interaction with an inducer, ixazomib exposure would be decreased):

 Strong CYP3A inducers: rifampin, rifapentine, rifabutin, carbamazepine, phenytoin, and phenobarbital

The following medicinal products and procedures are prohibited during the study:

- Excluded foods and dietaty supplement include Sr. John's wort and Ginkgo biloba
- Any antineoplastic treatment with activity against MM except for drugs in this treatment regimen.
- Radiation therapy (the requirement for local radiation therapy generally indicates disease progression).

 Platelet transfusions to help patients meet eligibility criteria are not allowed within 3 days before study drug dosing.

9.4 Precautions and Restrictions

- Fluid deficits should be corrected before and throughout treatment.
- Nonsteroidal anti-inflammatory drugs (NSAIDs) induced prevalence of nephrotoxicity is
 relatively low; however, given the wide use of these agents many persons are at risk,
 including for example, patients with cardio-renal disease, dehydration, and the aging kidney.
 NSAIDs should be avoided with impaired renal function given reported NSAID-induced renal
 failure in patients with decreased renal function.

Pregnancy

Thalidomide is known to be teratogenic.

It is not known what effects ixazomib citrate has on human pregnancy or development of the embryo or fetus. Therefore, female patients participating in this study should avoid becoming pregnant, and male patients should avoid impregnating a female partner. Nonsterilized female patients of reproductive age group and male patients should use effective methods of contraception through defined periods during and after study treatment as specified below.

Female patients must meet 1 of the following criteria:

- Postmenopausal for at least 1 year before the screening visit, OR
- Surgically sterile, OR
- If they are of childbearing potential, agree to practice 2 effective methods of contraception, at the same time, from the time of signing the informed consent form through 90 days after the last dose of study drug, AND
- Must also adhere to the guidelines of any treatment-specific pregnancy prevention program,
 if applicable, OR
- Agree to practice true abstinence when this is in line with the preferred and usual lifestyle of the subject. (Periodic abstinence [eg, calendar, ovulation, symptothermal, post-ovulation methods] and withdrawal are not acceptable methods of contraception.)

Male patients, even if surgically sterilized (ie, status postvasectomy), must agree to 1 of the following:

- Agree to practice effective barrier contraception during the entire study treatment period and through 90 days after the last dose of study drug, OR
- Must also adhere to the guidelines of any treatment-specific pregnancy prevention program,
 if applicable, OR

 Agree to practice true abstinence when this is in line with the preferred and usual lifestyle of the subject. (Periodic abstinence (eg, calendar, ovulation, symptothermal, post-ovulation methods] and withdrawal are not acceptable methods of contraception.)

9.5 Investigational Medicinal Product ixazomib citrate.

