8.1.1 Inclusion criteria

- Previously untreated patients with a confirmed diagnosis of symptomatic multiple myeloma according to IMWG criteria (see appendix A)
- Measurable disease according to the IMWG criteria (see appendix A)
 (If plasmacytoma is the only measurable parameter, the patient is not allowed to be included in the study, because of difficult response evaluation)
- Age ≥ 66 years or patients ≤ 65 years not eligible for ASCT
- WHO performance status 0-3 for patients <75 years and WHO performance status 0-2 for patients ≥ 75 years (see appendix D)
- Absolute neutrophil count (ANC) ≥ 1.0 x10⁹/l and platelet count ≥ 75x10⁹/l, unless related to bone marrow infiltration by malignant plasmacells
 Platelet transfusions to help patients meet eligibility criteria are not allowed within 3 days before study enrollment
- Written informed consent
- Patient gives consent for extra bone marrow and blood sampling
- Negative pregnancy test at study entry or at least 1 year post-menopausal or surgically sterile before study entry
- ◆ A female patient of childbearing potential, agrees to practice 2 effective methods of contraception, at the same time, from the time of signing the informed consent through 90 days after the last dose of study drug, AND must also adhere to the guidelines of any treatment-specific pregnancy prevention program (for thalidomide) OR agrees to completely abstain from heterosexual intercourse. (Periodic abstinence (eg, calendar, ovulation, symptothermal, post-ovulation methods) and withdrawal are not acceptable methods of contraception)

♦ Male patients, even if surgically sterilized, (i.e., status post vasectomy) must agree to practice effective barrier contraception during the entire study period and through 90 days after the last dose of study drug, AND must also adhere to the guidelines of any treatment-specific pregnancy prevention program (for thalidomide), OR agrees to completely abstain from heterosexual intercourse (Periodic abstinence (eg, calendar, ovulation, symptothermal, post-ovulation methods] and withdrawal are not acceptable methods of contraception).

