12.5 Pregnancies

Pregnancies of a female subject or the female partner of a male subject, occurring while the subject is on protocol treatment or within 90 days following the last dose of any drug from the protocol treatment schedule, should be reported to the sponsor. Pregnancies must be reported to the HOVON Data Center by fax within 24 hours after the event was known to the investigator, using the pregnancy report form provided.

If the subject is on study drug, the study drug is to be discontinued immediately and the subject instructed to return any unused portion of the study drug to the Investigator. The pregnancy, suspected pregnancy, or positive pregnancy test must be reported to the Sponsor who will inform the manufacturer immediately. All details should be documented on the pregnancy form CRF. The patient

should be referred to an obstetrician/gynaecologist experienced in reproductive toxicity for further evaluation and counseling.

The investigator will follow the female subject until completion of the pregnancy, and must notify the sponsor of the outcome of the pregnancy within 5 days or as specified below. The investigator will provide this information as a follow-up to the initial pregnancy report. If the outcome of the pregnancy meets the criteria for classification as a SAE (i.e., spontaneous or therapeutic abortion, stillbirth, neonatal death, or congenital anomaly - including that in an aborted fetus), the investigator should follow the procedures for reporting SAEs. In the case of a live "normal" birth, the sponsor should be informed as soon as the information is available. All neonatal deaths that occur within 30 days of birth should be reported, without regard to causality, as SAEs. In addition, any infant death after 30 days that the investigator suspects is related to the in utero exposure to the investigational medicinal product(s) should also be reported.

The investigator is encouraged to provide outcome information of the pregnancy of the female partner of a male subject, if this information is available to the investigator and the female partner gives her permission. The HOVON Data Center will forward all pregnancy reports within 24 hours of receipt to the Principal Investigator and the manufacturer of the investigational medicinal product Millennium The Takeda Oncology Company.

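### Section 9.4 joins barrier contraception and the pregnancy prevention programme by OR for men, where 8.1.1 requires both

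*Protocol*

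**What the plan says.** The male contraception rule appears twice in the protocol.

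- **Section 8.1.1 (inclusion criteria).** The rule for men begins "must agree to practice effective barrier contraception during the entire study period and through 90 days after the last dose of study drug, AND". The second duty, joined by that AND, is to follow any treatment-specific pregnancy prevention programme, which the criterion names as the one for thalidomide. Complete abstinence from heterosexual intercourse is the alternative to this pair.
- **Section 9.4 (Pregnancy).** The list opens with "Male patients, even if surgically sterilized (ie, status postvasectomy), must agree to 1 of the following". The first item is "Agree to practice effective barrier contraception during the entire study treatment period and through 90 days after the last dose of study drug, OR". The second is the prevention programme, if applicable, also ending in OR. The third is true abstinence.

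The female list in 9.4 handles the same step differently. For women of childbearing potential, two contraceptive methods are to be used "at the same time, from the time of signing the informed consent form through 90 days after the last dose of study drug, AND", and the programme follows as an added duty. Abstinence is again the alternative.

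Section 9.4 also states "Thalidomide is known to be teratogenic", and section 9.1.1 prescribes "a daily dose of thalidomide (100 mg) continuously" during induction.

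**The concern.** The two male rules cannot both apply. Section 8.1.1 asks for two measures together or abstinence, whereas 9.4 asks for any one of three. Section 9.4 is the text on precautions during treatment, so it is where a site would look when counselling a man already on thalidomide.

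A man who relied on the programme item alone would have no barrier duty in that list. He would have no 90-day period after the last dose either, because that period is written only into the barrier item. Section 12.5 nevertheless makes partner pregnancies reportable when they occur on treatment or "within 90 days following the last dose of any drug from the protocol treatment schedule", so the protocol treats those 90 days as a period of possible exposure.

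**Working it through.** The claim rests on the wording, not on a statistical figure, so the check is a comparison of the rules. Let B be barrier contraception through 90 days after the last dose, P the pregnancy prevention programme, and A abstinence.

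| Place | Logic |
|---|---|
| 8.1.1, men | (B AND P) OR A |
| 9.4, men | B OR P OR A |
| 9.4, women of childbearing potential | (two methods AND P) OR A |

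There are 2 × 2 × 2 = 8 combinations of B, P and A for men.

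- **8.1.1** accepts the 4 with A, plus the 1 with B and P but not A: 4 + 1 = 5.
- **9.4** accepts all but the one with none of the three: 8 − 1 = 7.
- **The difference** is 7 − 5 = 2 combinations: B alone and P alone.

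The male rule in 9.4 is therefore strictly weaker than 8.1.1. Three signs show which text is in error:

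1. 8.1.1 has AND at this point for men.
2. The female list in 9.4 has AND at the same point, although it too opens by asking for one of several criteria.
3. The programme item in the male list is still worded as something to be done *in addition*. That makes sense after AND but not as a stand-alone alternative.

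**Length of the thalidomide period.** Induction is 9 cycles of 28 days with daily thalidomide (9.1.1):

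- 9 × 28 = 252 scheduled days, without delays.
- 252 + 90 = day 342 including the tail, for a patient who stops after induction.

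In maintenance, "maintenance treatment with either ixazomib citrate or placebo will be started" without thalidomide (9.2.1). The inconsistency in 9.4 does not end there, however. The barrier duty runs to 90 days after the last dose of study drug, and section 9.5.1 warns of possible harm to the unborn child from ixazomib as well. The 252 and 342 days describe the thalidomide-specific window only.

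**The case against.** The strongest reply is that the stricter rule already binds every enrolled man. Section 8.1.1 covers the whole study period plus 90 days. Section 8.1.2 excludes anyone unable or unwilling to use adequate contraception. Under 15.2.1, all eligibility criteria are checked against a list at registration, and discussion of the Risk Management Program with the patient is recorded. Nothing in 9.4 claims to relax these criteria. This stands, and it lowers the practical risk considerably.

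Section 9.4 also says, before the lists, that men should avoid fathering a child and should use effective contraception during and after treatment. This softens the literal reading, but the sentence refers to the lists below it for its content, so it does not repair the male list.

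The content of the thalidomide programme is not reproduced in the protocol, so a man following it alone may in fact be told to use barrier protection. That is fair: the documents show a gap in the instruction in 9.4, not a demonstrated gap in protection.

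Finally, this is a drafting error that touches no endpoint, sample size or analysis. That is true, but it does not make the two rules compatible.

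**Conclusion.** The concern holds. The male contraception rule in 9.4 is wrong as written: it contradicts 8.1.1 and departs from the female list in the same section. It admits two single-measure routes that 8.1.1 does not.

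Its size is that of an inconsistent safety instruction for a teratogenic drug, bearing on a scheduled thalidomide period of 252 days (to day 342 with the tail). Those figures assume no delays, and day 342 also assumes that treatment stops after induction. The number of men with partners of childbearing potential is not given, so no event rate can be stated. The entry criteria reduce the risk, but a site reading 9.4 during treatment would still find a looser rule than the patient accepted. It should be corrected. No statistical result depends on it.

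**What to change.** In the male list of 9.4, replace the first OR with AND. The rule then requires barrier contraception through 90 days after the last dose together with the pregnancy prevention programme, if applicable, or else true abstinence. This brings its logic into line with 8.1.1 and with the female list.

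Two smaller wording differences would remain and could be settled in the same edit:

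- 8.1.1 refers to the study period, while 9.4 refers to the study treatment period.
- 8.1.1 asks for complete abstinence, while 9.4 asks for true abstinence in keeping with the patient's usual lifestyle.

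The essential change is one connecting word. It has no effect on design, sample size or analysis.

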9.5.1 Summary of known and potential risks

The emerging safety profile indicates that ixazomib citrate is generally well tolerated with manageable and reversible AEs with both the IV and PO formulations

The most frequent (at least 20%) TEAEs reported with the PO formulation pooled from combination trials irrespective of the combination and irrespective of causality to ixazomib citrate, include fatigue (39%), nausea (33%), constipation (30%), thrombocytopenia (29%), vomiting (26%), diarrhea (23%), anemia (23%), peripheral edema (21%), fever (20%), and neutropenia (20%).

Ixazomib citrate may be harmful to the unborn child.

For al full overview of toxicity reported with ixazomib citrate treatment we refer to the Investigator's Brochure.

9.5.2 Preparation and labeling

Ixazomib citrate will be labeled as an Investigational Medicinal Product.

The ixazomib citrate capsules will be provided by Millennium. The study drug will be labeled.

Packaging labels will fulfill all requirements specified by governing regulations.

The ixazomib citrate capsule formulation consists of drug substance, microcrystalline cellulose, talc, and magnesium stearate. The capsules are individually packaged in cold form foil-foil blisters. The 2.3-, 3.0-, and 4.0 mg capsules used in this trial are supplied as a 1 x 3 blister card in a child-resistant cardboard wallet. Each capsule strength has a unique color. Dosage strength is stated as the active boronic acid.

Capsules should be stored unopened at 2-8°C (36-46°F) and must be administered as intact capsules and are not intended to be opened or manipulated in any way.

9.5.3 Storage and handling

Ixazomib citrate is an anticancer drug and as with other potentially toxic compounds caution should be exercised when handling ixazomib citrate capsules.

Upon receipt at the investigative site, ixazomib citrate should remain in the blister and carton provided until use or until drug is dispensed. The container should be stored at the investigative site refrigerated (36°F to 46°F, 2°C to 8°C). Ensure that the drug is used before the retest expiry date provided by Millennium. Expiry extensions will be communicated accordingly with updated documentation to support the extended shelf life.

In countries where local regulations permit, ixazomib citrate capsules dispensed to the patient for take-home dosing should remain in the blister packaging and refrigerated as noted above until the point of use. The investigative site is responsible for providing the medication to the patient in the correct daily dose configurations. Comprehensive instructions should be provided to the patient in order to ensure compliance with dosing procedures. Patients who are receiving take-home medication should be given only 1 cycle of medication at a time. Patients should be instructed to store the medication refrigerated (36°F to 46°F, 2°C to 8°C) for the duration of each cycle. Any extreme in temperature should be reported as an excursion and should be dealt with on a case-by-case basis. Because ixazomib citrate is an investigational agent, it should be handled with due care. Patients should be instructed not to chew, break, or open capsules. In case of contact with broken capsules, raising dust should be avoided during the clean-up operation. The product may be harmful by inhalation, ingestion, or skin absorption. Gloves and protective clothing should be worn during cleanup and return of broken capsules and powder to minimize skin contact.

The area should be ventilated and the site washed with soap and water after material pick-up is complete. The material should be disposed of as hazardous medical waste in compliance with federal, state, and local regulations.

In case of contact with the powder (eg, from a broken capsule), skin should be washed immediately with soap and copious amounts of water for at least 15 minutes. In case of contact with the eyes, copious amounts of water should be used to flush the eyes for at least 15 minutes. Medical personnel should be notified. Patients are to be instructed on proper storage, accountability, and administration of Ixazomib, including that ixazomib citrate is to be taken as intact capsules.

